# 5.2 AEs coding/grading

Adverse events are coded using the Medical dictionary for regulatory activities (MedDRA) terminology.

AEs will be assessed according to the Common Terminology Criteria for Adverse Events (CTCAE) version 5.0.

CTCAE grading is by definition a 5-point scale generally corresponding to mild, moderate, severe, life threatening, and death. This grading system inherently places a value on the

importance of an event, although there is not necessarily proportionality among grades (a grade 2 is not necessarily twice as bad as a grade 1).

# 5.3 Laboratory parameters derivations

Grade categorization of lab values will be assigned programmatically as per NCI Common Terminology Criteria for Adverse Events (CTCAE) version 5.0 (specify version used in the RAP). The calculation of CTCAE grades will be based on the observed laboratory values only, clinical assessments will not be taken into account. The criteria to assign CTCAE grades are given in Novartis internal criteria for CTCAE grading of laboratory parameters. The latest available version of the document based on the underlying CTCAE version 5.0 at the time of analysis will be used. For laboratory tests where grades are not defined by CTCAE v5.0, results will be graded by the low/normal/high (or other project-specific ranges, if more suitable) classifications based on laboratory normal ranges.

A severity grade of 0 will be assigned for all non-missing lab values not graded as 1 or higher. Grade 5 will not be used. For laboratory tests that are graded for both low and high values, summaries will be done separately and labelled by direction, e.g., sodium will be summarized as hyponatremia and hypernatremia.

### **Imputation Rules**

CTC grading for blood differentials is based on absolute values. However, this data may not be reported as absolute counts but rather as percentage of WBC.

If laboratory values are provided as '<X' (i.e. below limit of detection) or '>X', prior to conversion of laboratory values to SI unit, these numeric values are set to X.

The following rules will be applied to derive the WBC differential counts when only percentages are available for a xxx differential

```
xxx count = (WBC count) * (xxx %value / 100)
```

Further derivation of laboratory parameters might be required for CTCAE grading. For instance, corrected calcium can be derived using the reported total calcium value and albumin at the same assessment using the following formula:

Corrected Calcium (mmol/L) = Calcium (mmol/L) + 0.02 [40 (g/L) - Albumin (g/L)]

For calculation of laboratory CTC grades 0 and 1, the normal range for derived corrected calcium is set to the same limits (in mg/dL) as for calcium.

CTC grades for the derived absolute WBC differential counts (neutrophils, lymphocytes) and corrected calcium will be assigned as described above for grading

#### 5.4 Statistical models

## 5.4.1 Analysis supporting primary objective(s)

For region-level CLR, statistical model details are presented in Section 2.5. The GLIMMIX procedure in SAS will be used to implement the logistic regression model with random effects.

This analysis will be restricted to participants with at least one PET positive region (TP or FP) by central assessments in the EFF. In case of problems with fitting the model and estimating parameters, the default estimation technique (i.e. residual pseudo-likelihood with a subject expansion (METHOD = RSPL)) will be used. This analysis will be applied to each of the three central readers via the (BY READER) statement.

For this model, the SAS code will be:

```
proc glimmix data=dataset;
by reader;
  class subject;
  model tpcount / poscount= / solution;
  random intercept / subject=subject;
run;
```

- tpcount refers to the number of TP regions per participant
- poscount refers to the number of PET positive regions (TP or FP) per participant

The estimated fixed effect  $\hat{\mu}$  and its standard error SE on the logit scale can be obtained from the output. And the (subject-specific) region-level CLR (conditional on the random effect when  $b_i = 0$ ) along with the two-sided 95% CI can be computed by applying the inverse link function:

Point estimate of the region-level CLR: 
$$E[p_{i}|\hat{b}_{i}=0] = E\left[\frac{y_{-}i}{n_{-}i}|\hat{b}_{i}=0\right] = \frac{\exp(\hat{\mu})}{1+\exp(\hat{\mu})}$$

$$CI_{Lower} = \frac{\exp(\hat{\mu}-z_{0.975}SE)}{1+\exp(\hat{\mu}-z_{0.975}SE)}$$

$$CI_{Upper} = \frac{\exp(\hat{\mu}+z_{0.975}SE)}{1+\exp(\hat{\mu}+z_{0.975}SE)}$$

For patient-level PPV, an exact binomial confidence interval (implemented using SAS procedure FREQ with EXACT statement for one-way tables) will be calculated (Clopper and Pearson 1934)

[figure not shown]
Efficacy endpoints be summarized in terms of percentage rates with 95% CIs.

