12.4.2 Statistical model, hypothesis, and method of analysis

To address the co-primary efficacy objectives:

Region-level CLR and its 95% CI will be calculated using logistic random-effects models taking into account the correlation among regions within one patient. .The lower bound of the 95% CI for CLR should be greater than 0.5 to attain the first co-primary endpoint.

Patient-level PPV and its 95% CI will be calculated based on the binomial distribution. The lower bound of the 95% CI for patient-level PPV should be greater than 0.2 to attain the second co-primary endpoint.

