#### Primary estimand 1:

- 1. Population: Patients with biopsy proven prostate adenocarcinoma and rising PSA after definitive therapy with RP or curative-intent radiation therapy (external beam or brachytherapy), diagnosed of biochemically recurrent prostate cancer. Further details about the population are provided in the protocol Section 5.
- 2. Variable: Regional-level correct localization rate (CLR), defined as the proportion of regions containing at least one true positive lesion (anatomically localized correspondence between [18F]CTT1057 PET imaging and the reference standard), regardless of any coexistent false positive findings within the same region, out of all regions containing at least one [18F]CTT1057 PET-positive finding, using central reads.
- 3. Treatment of interest: [18F]CTT1057 injected as a single intravenous dose of approximately 370 MBq and subsequent PET/CT scan. Further details about the investigational treatment is provided in the protocol Section 6.
- 4. Intercurrent events: Participants who received the investigational imaging agent [18F]CTT1057 but did not undergo/complete the PET scan for any reasons (e.g. consent withdrawal, PET camera failures, etc.). Details on how to handle intercurrent events are provided in Section 2.5.3.
- 5. Summary measure: Region-level CLR along with two-sided 95% confidence interval estimated using logistic random-effects models taking into account the correlation among regions within one participant.

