#### 2.5.1 **Primary endpoint(s)**

The co-primary endpoints evaluated for participants in the EFF are the following:

Region-level CLR: Proportion of regions containing at least one TP lesion (anatomically localized correspondence between PET imaging and the reference standard), regardless of any co-existent FP findings within the same region, out of all regions containing at least one PETpositive finding by central assessments. See Section 1.2.1 for Primary Estimand.

Patient-level PPV: Proportion of participants who have at least one TP lesion (anatomically localized correspondence between PET imaging and the reference standard), regardless of any co-existent FP findings, out of all participants who are PET/CT scan positive by central assessments. See Section 1.2.1 for Primary Estimand.

Centralized imaging assessments (CTS Level 2) will be used as reference standard if pathology assessment (CTS Level 1) is not available for a lesion, inconclusive or negative (for biopsy only).

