Change in patient management plans attributed to the [18F]CTT1057 PET/CT scan is defined as the percentage of participants who undergo a change in intended treatment plan attributed to

the PET/CT scan as assessed by pre-imaging questionnaire 1 and post-imaging questionnaire 2.

The number and percentage of participants from the F-SAF for each of the following categories of treatment plan in each of the two questionnaires will be calculated: surgery, radiation alone, radiation alone with change in radiation treatment plan (only applicable for questionnaire 2), radiation plus ADT, ADT alone, observation/surveillance, other (free text box).

Treatment plan change is defined as a change in the pair of categories (one category of questionnaire 1, one category of questionnaire 2).

The number and percentage of participants from the F-SAF with treatment plan change as defined above will be calculated. Shift tables comparing treatment plans between questionnaire 1 and 2 will be displayed. The number (%) of participants with and without a change in treatment plans by [18F]CTT1057 local read results (i.e. positive, negative, and inconclusive) will be tabulated.

**Region-level sensitivity** is defined as the proportion of TP regions among those that are TP or FN

**Region-level specificity** is defined as the proportion of TN regions among those that are TN or FP

**Region-level negative predictive value** is defined as the proportion of TN regions among those that are TN or FN

**Region-level accuracy** is defined as the proportion of TP and TN regions among those that are identified on [18F]CTT1057 (regardless of TP, TN, FP, FN)

where TP, TN, FP, FN regions are defined as follows:

- PSMA TP regions are regions containing at least one TP lesion (anatomically localized correspondence between [18F]CTT1057 PET imaging and the CTS).
- PSMA TN regions are regions containing no lesions with pathological [18F]CTT1057 uptake and confirmed by CTS.
- PSMA FP regions are regions containing lesions with pathological [F]CTT1057 uptake but are verified negative by CTS or none is correctly localized in anatomical location by the CTS.
- PSMA FN regions are regions containing no lesions with pathological [F]CTT1057 uptake but are confirmed as having at least one lesion with the CTS.

Number of TP, TN, FP, FN regions will be presented and used to calculate the diagnostic performance parameters.

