Two-sided 95% CIs for (overall) region-level diagnostic performance parameters will be calculated using a logistic random-effects models taking into account the correlation among regions within a participant.

For different regions (i.e. prostate region, PLN, extra-pelvic lymph nodes, skeletal, and visceral), two-sided exact binomial 95% CIs for region-level diagnostic performance parameters will be calculated.

Concordance between [18F]CTT1057 and [68Ga]Ga-PSMA-11 for detection of lesions and positive percent agreement will be calculated to assess the concordance.

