### 5.4.2 Analysis supporting secondary objective(s)

For region-level efficacy endpoints, statistical model details are presented in section 2.6. The GLIMMIX procedure in SAS will be used to implement the logistic regression model with random effects.

For patient-level efficacy endpoints, an exact binomial confidence interval (implemented using SAS procedure FREQ with EXACT statement for one-way tables) will be calculated (Clopper and Pearson 1934)

Efficacy endpoints be summarized in terms of percentage rates with 95% CIs.

Confidential

Novartis

Page 51 of 56

Confidential

[figure not shown]
Novartis

Page 52 of 56

Confidential

Novartis

Page 53 of 56

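### SAP 5.4.1 reports CLR at a zero random effect, not as the defined proportion; the 0.50 decision is essentially unchanged, but PPA and the overall region-level secondary intervals would miss their targets if the formula is reused, and the named fallback is the fit already coded

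*SAP*

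**What the plan says.** SAP 2.5.1 defines the first co-primary endpoint as a "Proportion of regions containing at least one TP lesion", taken over all regions with a PET-positive finding. The summary measure of primary estimand 1 (SAP 1.2.1) is "Region-level CLR along with two-sided 95% confidence interval estimated using logistic random-effects models", and protocol 12.4.2 names the same model: "Region-level CLR and its 95% CI will be calculated using logistic random-effects models taking into account the correlation among regions within one patient". Success requires a lower limit above 0.50.

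SAP 5.4.1 fits a random-intercept logistic model and applies the inverse logit to the fixed intercept and its Wald limits. It calls the result "the (subject-specific) region-level CLR (conditional on the random effect when" `b_i` = 0). The printed GLIMMIX call has no METHOD= option. For fitting problems the section says that "the default estimation technique (i.e. residual pseudo-likelihood with a subject expansion (METHOD = RSPL)) will be used".

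For the overall secondary measures, SAP 2.6.1 says: "Number of TP, TN, FP, FN regions will be presented and used to calculate the diagnostic performance parameters". Their intervals are a different matter: those for "region-level diagnostic performance parameters will be calculated using a logistic random-effects models". SAP 2.6.2 takes both the estimate and the interval for lesion-level PPA from a model of the same form. On implementation SAP 5.4.2 only refers back: "For region-level efficacy endpoints, statistical model details are presented in section 2.6". Section 2.6 gives no back-transformation.

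SAP 2.5.5 adds an equal-weight participant-level CLR as a sensitivity analysis. SAP 2.6.5 plans no sensitivity analysis for secondary endpoints.

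**The concern.** With a normal random intercept, the inverse logit of the mean intercept describes a participant whose random effect is zero. It is not the proportion over all regions, except at 0.50. Above 0.50 it is higher than that proportion, and the gap grows with the within-participant correlation and with distance from 0.50.

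For CLR the decision is taken at 0.50, so the issue is the reported value and interval. For the secondary measures nothing planned would reveal a difference. If a programmer reuses the 5.4.1 formula, the only one in the visible text, PPA would be too high. The intervals placed beside the count-based sensitivity, specificity, NPV and accuracy would be centred on another quantity.

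The fallback is a separate matter. If the co-primary model fails to fit, the SAP sends the analyst back to the same fit.

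**Working it through.** **The plan's own figures.** Beta(1,1) has variance 1/12. n = (1/12) × (1.960 + 1.282)² / 0.08² = 136.8, so 137; 137/0.80 = 171.25, so 172. Power at 152 evaluable is 92.7%. All three match SAP section 3. Beta(1,1) also implies an intraclass correlation (ICC) of 1/(1+1+1) = 1/3.

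**The decision.** The inverse logit of μ exceeds 0.5 exactly when μ > 0. By symmetry of the normal intercept, so does the population proportion. The two scales therefore give the same hypothesis at 0.50.
- Simulated chance of a lower limit above 0.50 at a true value of 0.50: 1.6–2.5% for the coded model and 1.7–2.6% for a clustered proportion. A second set of runs gave 1.8–3.4% for the model.
- At the planned alternative of 0.58 the two methods differ by at most 1.3 percentage points.
- If the TP rate depends on the number of positive regions (assumed log-odds slope −0.3 to +0.3 per extra region, pooled CLR exactly 0.50), the model passes in 4.0% to 1.8% of runs, against 2.6–2.9% for the pooled proportion.

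**The two scales by integration, ICC 1/3.**

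| Population proportion | Value at `b_i` = 0 |
|---|---|
| 0.50 | 0.500 |
| 0.58 | 0.619 |
| 0.80 | 0.899 |
| 0.90 | 0.975 |

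**The coded fit.** Residual pseudo-likelihood (RSPL) shrinks the random-effect variance, so its estimates fall between the two columns. It was simulated with purpose-written code, not SAS: one events/trials record per participant, z = 1.96, beta-binomial data, 2000 replicates per cell. Inputs from the plan are 152 evaluable participants, 80% PET-positive (152 × 0.80 ≈ 122) and five regions. The true rates, the ICC range and all other counts per participant are assumptions.

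Coverage of the 5.4.1 interval at true 0.80:

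| Measure | Units per participant | ICC 1/3 | ICC 0.2 | ICC 0.1 |
|---|---|---|---|---|
| Accuracy (n = 152) | 5 regions | 63% | 86% | 94% |
| Specificity or NPV | 3–5 regions | 75% | 89% | 95% |
| Sensitivity (n = 122) | mostly 1–2 regions | 94–96% | 94–96% | 94–96% |
| CLR (n = 122) | mostly 1–2 regions | 95% | 95% | 95% |
| CLR (n = 122) | 1–5 regions | 87% | 92% | 96% |
| PPA (n = 122) | 1–5 lesions | 87% | 92% | 94% |
| PPA (n = 122) | 1–20 lesions, skewed, mean 3.9 | 80% | 89% | 94% |

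- A participant-clustered interval covers 94–96% in every cell. In a further PPA run (1–15 lesions, ICC 1/3) it covered 92–93%, still above 80–87% for the back-transformation.
- The accuracy interval is centred at 0.837, 0.818 and 0.806 at the three ICCs. PPA in the skewed case is estimated at 0.832, 0.817 and 0.806.
- Repeat runs of the accuracy row, including logit-normal data as in the SAP's model, gave 61–65%, 84–88% and 93–95%. About 64/85/94% is a fair summary.
- At true 0.90 the accuracy interval covers 56/81/92%, with 8.8% of fits not converging at ICC 1/3 and excluded.

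**Estimation method.** With a quadrature likelihood fit, five regions and ICC 1/3, a true 0.80 is estimated at 0.898 and coverage is 6%. The METHOD= choice therefore affects the reported figure.

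**Fallback.** By the SAP's own wording RSPL is the default. The code names no method, so it already runs RSPL.

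**The case against.** The strongest reply is that the primary conclusion is safe and the rest is reporting detail. Much of that stands.

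- SAP 5.4.1 already labels its CLR output subject-specific and conditional, the protocol names the model, the TP and FP region counts will be shown, and SAP 2.5.5 supplies a population-level CLR.
- A reader might infer that secondary sensitivity, specificity, NPV and accuracy will be overstated. They will not: SAP 2.6.1 and 2.6.2 calculate them from counts. Only their intervals are at issue, and biased estimates concern PPA alone.
- A reader might also infer that the SAP prescribes the `b_i` = 0 formula for secondary endpoints. The visible text does not. Pages after 5.4.2 are not shown and a cross-reference in the PPA paragraph is broken, so a formula could stand there.
- ICC 1/3 is a sizing placeholder for CLR, chosen because nothing was known. The documents give no expected accuracy or PPA and no lesion counts. At ICC 0.1 the tabulated coverage is 94–96%.

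What the reply does not remove: SAP 2.5.5 covers CLR only, no secondary sensitivity analysis is planned, the plan says it has no information on the correlation and so cannot presume a low one, and the fallback is empty on the SAP's own terms.

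**Conclusion.** The point holds in a limited form. The 5.4.1 formula does not estimate the defined proportion except at 0.50. It would be tempting to conclude that the CLR test is invalid. The documents do not support that: the threshold lies where the two scales meet, and the only shift found was small (1.8–4.0% against a nominal 2.5%) and required the TP rate to vary with the number of positive regions.

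The reported CLR and its interval are off-target mildly or not at all when participants have one or two positive regions, and more so with up to five. If the formula is reused, PPA would be about 0.83 for a true 0.80 at ICC 1/3 in the skewed-lesion case, and the accuracy interval would cover about 64/85/94% at the three ICCs. These sizes rest on assumed true rates, correlations and counts per participant, and on simulation code that is not SAS. The empty fallback needs no assumption. The changes should be made, but they do not threaten the primary conclusion.

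**What to change.** - **SAP 2.5.2 and 5.4.1.** Keep the protocol-named model and the 0.50 rule for the CLR decision. Beside it, report total TP regions divided by total PET-positive regions, with a participant-clustered 95% CI (GEE, independence working correlation, robust standard error), next to the 2.5.5 estimate. State that the pooled figure weights regions and the 2.5.5 figure weights participants. They can differ: with 60/30/10% of participants having 1/2/3 regions, and CLR 0.70 for one region and 0.85 for two or three, pooled is (0.6 × 0.70 + 0.9 × 0.85)/1.5 = 0.79 and equal-weight is 0.6 × 0.70 + 0.4 × 0.85 = 0.76.
- **SAP 2.6.2 and 5.4.2.** Report PPA as the observed proportion with a participant-clustered 95% CI. Use participant-clustered CIs for the count-based overall region-level sensitivity, specificity, NPV and accuracy.
- **Fitting.** State METHOD= for the primary fit and name a fallback that differs from it, for example the clustered proportion.
- **SAP section 4.** Record the change.

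The cost is SAP wording and a few lines of code before database lock, with no new data. There is one small documented departure: protocol 12.5.1 names random-effects models for the overall region-level CIs. The clustered CI still accounts for correlation within participants. The visible protocol text names no model for PPA, and the CLR decision does not change.

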### 5.4.2 Analysis supporting secondary objective(s)

For region-level efficacy endpoints, statistical model details are presented in section 2.6. The GLIMMIX procedure in SAS will be used to implement the logistic regression model with random effects.

For patient-level efficacy endpoints, an exact binomial confidence interval (implemented using SAS procedure FREQ with EXACT statement for one-way tables) will be calculated (Clopper and Pearson 1934)

Efficacy endpoints be summarized in terms of percentage rates with 95% CIs.

Confidential

Novartis

Page 51 of 56

Confidential

[figure not shown]
Novartis

Page 52 of 56

Confidential

Novartis

Page 53 of 56

